For assessment of passive glenohumeral internal rotation, participants laid supine with 90° of shoulder abduction in the frontal plane and the elbow flexed at 90°. ¹¹ The examiner stabilized the scapula with one hand by applying mild pressure to its anterior aspect (coracoid process), while applying with the other hand a passive movement of shoulder internal rotation to its maximal point. An assistant read the measurement placing the goniometer with the stationary arm parallel to the floor and the mobile arm in alignment with the forearm starting at the olecranon.³⁹ The same starting posture and goniometer positioning will be used for measuring passive glenohumeral external rotation.

Experimental conditions (independent variables)

There are two independent variables in the research design: treatment condition and time (pre-, post-application). Treatment condition has three levels, which include the AP shoulder mobilization, a manual contact and a no-contact condition.⁴⁷ These experimental conditions will be administered in random order in three separated sessions to all participants, with each session separated by 48 h in order to control for carry-over effects.³⁵ The treatment allocation sequence will be randomized using sealed envelopes and concealed from the investigator who took the outcome measurements. An experienced physiotherapist with a Master degree on manual therapy and more than 10 years of working experience will apply all conditions. This physiotherapist will be blinded to the results of the measurements and questionnaires used as outcome measures.

All conditions will be applied for a total of 10 min, comprising three sets of 3 min, alternating with 30-s rests. Verbal instructions and positioning will be strictly standardized during all the sessions.

Treatment condition

The treatment condition consist on the application of a passive rhythmic AP mobilization to the glenohumeral joint of the affected shoulder. In particular, a Grade III AP glide to the humeral head with the arm positioned in 90° of glenohumeral abduction and full internal rotation was used.⁴⁷ The posterior gliding force to the humeral head was applied maintaining the glide at right angles to the plane of movement and at a frequency of 2 Hz which will be controlled by means of a metronome. The arm will be returned to its original position between each set.

Manual contact condition

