During the manual contact condition the therapist positione the patient in a mid-range position of glenohumeral abduction and internal rotation and apply the hands to the same contact point as in the treatment condition. However, a simulated posterior glide will be performed but with minimal pressure actually applied.⁴⁷ The number of repetitions and sets were as per the treatment condition.

No-contact condition

During the no-contact condition, the subject remain in the initial starting position thorough the entire session but there are no manual contact between the therapist and the participant.⁴⁷ The total treatment time will be the same as per the other conditions.

Procedure

At the first session and after recording demographic data, the NRPS and DASH will be administered followed by PPT, ROM and muscle strength measurements in a standardized order. Subjects then will received the assigned intervention for that session and, immediately afterwards, all outcome measures will be reassessed following the same order as before. The only exception was the DASH, which will be assessed before and 24 hours after each experimental condition. This procedure will be repeated for all the three test sessions.

An investigator, will blinded to the allocated intervention, performed all the outcome measures before and immediately after the application of the three experimental conditions. Discussion between researchers and subjects will be minimized during treatment in order to facilitate subject blinding and reduce potential interactions. No feedback will be given on performance until after the final session. The extent of subject blinding will be assessed through a short, self-administered, post-experiment questionnaire, where participants will be asked to indicate whether they have experienced a physiotherapy treatment in any of the sessions and, if so, in which session.³⁵

Statistical analysis

Data will be analysed using SPSS 22 for Windows. Statistical significance will be set at $p < 0.05$.

Two independent variables will be incorporated into the research design: treatment (AP mobilization, manual contact, no-contact) and time (pre- and post-intervention). Five dependent variables will be considered including PPT, muscle strength, NRPS, DASH (disability/symptom section) and ROM.

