Descriptive statistics will be calculated to describe baseline data. A two-way analysis of variance (ANOVA) through a General Linear Model and appropriate post-hoc tests of simple effects will be used to evaluate hypothesis that AP mobilization produced more changes than manual contact and no-contact conditions from pre- to post-intervention ($P=0.05$). The between subject factor will be treatment condition (AP mobilization, manual contact, no-contact) with time (pre and post-intervention) as within subject factors.

Sphericity will be confirmed by means of Mauchly's test. Bonferroni test will be used for multiple comparisons and the effect size will be estimated using Eta square (η^2) when significant. An effect size of 0.01 will be considered small, 0.06 medium and 0.14 large.⁷

REFERENCES

7. Cohen J. *Statistical Power Analysis for the Behavioral Sciences.* New York, NY: Routledge Academic, 1988.

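### The Mauchly step tests nothing in the declared model and cannot confirm sphericity in the crossover actually run; condition should be within-subject, with a corrected F and paired contrasts

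*Protocol*

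**What the plan says.** Three statements in the protocol bear on this.

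- **Design** (Experimental conditions): "These experimental conditions will be administered in random order in three separated sessions to all participants". The same section says "Treatment condition has three levels, which include the AP shoulder mobilization, a manual contact and a no-contact condition". Time has two levels, before and after application.
- **Model** (Statistical analysis): "The between subject factor will be treatment condition (AP mobilization, manual contact, no-contact) with time (pre and post-intervention) as within subject factors".
- **Assumption check** (Statistical analysis): "Sphericity will be confirmed by means of Mauchly's test".

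The significance level is 0.05, and "Bonferroni test will be used for multiple comparisons". The protocol names no epsilon correction or multivariate test. It states no sample size, no standard deviation of change for any condition, and no correlation between a participant's changes across sessions.

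**The concern.** The sphericity sentence fails on either reading of the plan.

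Taken literally, the only within-subject factor has two levels. Sphericity then holds by construction and the step checks nothing.

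Taken in line with the design, condition is a three-level within-subject factor and sphericity can fail. It would fail, for instance, if response to the AP glide varied more between people than change under the control conditions. A non-significant Mauchly test is then only a failure to detect a departure, and the word confirmed claims more than the test can deliver.

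At stake is the error rate of the condition-by-time test, which carries the main hypothesis for each of the five dependent variables. More basic is which F test is meant at all, because the declared model and the design imply different error terms.

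**Working it through.** **Inputs from the protocol.** Three conditions, two time points, all participants in all conditions, level 0.05. There is no stated error rate or sample size to reproduce beyond the nominal 5%.

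**Assumptions (not in the protocol).** Sample size n = 10, 15, 20, 30. Ratio r of the SD of change under AP to that under each control = 1, 1.5, 2, 3. Correlation ρ of changes between sessions = 0, 0.3, 0.5. Normal data, no treatment effect.

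**Step 1: is there anything to test?** With k orthonormal contrasts, Mauchly's test has k(k+1)/2 − 1 degrees of freedom.
- Time only (k = 1): 1 − 1 = 0. The test is empty.
- Condition within-subject (k = 2): 3 − 1 = 2. The test exists.

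**Step 2: how far can sphericity fail?** With two time points, the condition-by-time test is an ANOVA of the pre-post changes. Let M be the covariance matrix of the two orthonormal contrasts. Then ε = (tr M)² / (2 tr M²). For r = 2 and ρ = 0, the contrast variances are (4+1)/2 = 2.5 and (4+1+4)/6 = 1.5, and their covariance is (4−1)/√12 = 0.866. So tr M = 4, tr M² = 6.25 + 2.25 + 2(0.75) = 10, and ε = 16/20 = 0.80. For r = 3 and ρ = 0, ε = 0.654.

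**Step 3: true error at nominal 5%, condition within-subject.** Results are from 100,000 simulated trials per setting. Ranges cover n = 10-30 and ρ = 0-0.5.

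| r | Uncorrected F | Mauchly, then Greenhouse-Geisser if significant | Greenhouse-Geisser always |
|---|---|---|---|
| 1 | 4.9-5.1% | 4.8-5.0% | 4.0-4.7% |
| 1.5 | 5.3-5.5% | 5.1-5.3% | 4.3-4.8% |
| 2 | 6.0-6.4% | 5.0-5.8% | 4.6-4.9% |
| 3 | 7.0-7.8% | 4.9-6.0% | 4.9-5.2% |

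The row r = 1 is the check: the uncorrected F holds its level when SDs are equal.

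**Step 4: how often does Mauchly detect the departure?** Ranges are over ρ.

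| r | n = 10 | n = 20 | n = 30 |
|---|---|---|---|
| 1.5 | 10-11% | 18-23% | 27-35% |
| 2 | 23-32% | 52-68% | 73-87% |
| 3 | 60-77% | 94-99% | over 99% |

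**Step 5: the F test as literally written.** Treating condition as between-subject gives F(2, 3n−3). With equal SD σ, the expected mean square for condition is σ²(1−ρ) and for error σ², so F is scaled by 1−ρ. At ρ = 0.5 the rejection rate is roughly P(F(2, 2(n−1)) > 2 × critical value). That is 0.67% at n = 10 (critical value 3.354), 0.43% at n = 20 (3.159) and 0.36% at n = 30 (3.101). Simulation gives 0.61%, 0.41% and 0.34%.

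| r | ρ = 0 | ρ = 0.3 | ρ = 0.5 |
|---|---|---|---|
| 1 | 5.0% | 1.5-1.8% | 0.3-0.6% |
| 2 | 6.2-6.4% | 3.0-3.4% | 1.5-1.9% |
| 3 | 7.2-7.8% | 4.6-5.3% | 3.3-3.9% |

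The excess at ρ = 0 comes from unequal variances in a between-group ANOVA, not from sphericity.

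**Step 6: the AP-versus-control comparison.** I simulated 60,000 trials per setting at n = 10, 20 and 30, two-sided 5%, before Bonferroni. A paired t test of the difference in change, using its own standard error, rejects in 4.8-5.2% of trials. The same comparison using the pooled between-subject error rejects in 0.7% (r = 1, ρ = 0.5) to 10% (r = 3, ρ = 0).

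**The case against.** The strongest reply is that the model the protocol writes has no sphericity problem, so inflation figures for a within-subject F describe a different analysis. That stands. A reader might infer that the planned test runs above 5%. The documents do not support this: as written it is conservative in most settings with positively correlated changes, and the 5.3-7.8% applies only once condition is made within-subject.

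A reader might also infer that Mauchly has little power at this trial's sample size. No sample size is given, and power depends heavily on the assumed SD ratio: at r = 3 it is already 60-77% with 10 participants. It is low mainly where the inflation is small.

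A third tempting claim is that the error concentrates in trials that pass Mauchly. The conditional rate is indeed higher there, but the subset can be tiny. At r = 3, n = 20, ρ = 0, 5.9% of trials pass and 12.8% of those reject. That is 0.059 × 0.128 = 0.75% of all trials, against 7.1% overall, or about one false positive in nine.

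Finally, the action after a significant Mauchly test is ordinary SAP detail, and the SAP is not shown. Its absence is no finding, and silence does not mean that the uncorrected F would be used. The usual two-step routine also stays within 4.8-6.0%. What remains is what the protocol itself fixes: a factor declaration that conflicts with its design, and a check that is empty under that declaration and over-claims under the design.

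**Conclusion.** The point holds in limited form. The contradiction over the condition factor, and the emptiness of the Mauchly step in the declared model, follow from the text without any assumption.

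The sizes rest on assumed n, SD ratios and correlations. Under these the uncorrected within-subject F exceeds its level by about 0.3 to 2.8 percentage points. Moving from the two-step routine to unconditional Greenhouse-Geisser lowers the error by about one point at most. The larger numerical consequence is the choice of error term. The literal analysis can reject in well under 1% of null trials when changes are correlated, which would make a real effect hard to detect, and its pooled AP-versus-control comparison can miss its level in either direction.

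Overall this is a minor to moderate point, best handled as part of correcting the between-subject declaration.

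**What to change.** In the protocol's Statistical analysis section:

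1. Declare condition (three levels) and time (two levels) both as within-subject factors, in line with the design.
2. Replace the Mauchly sentence with a statement that the condition-by-time test uses the Greenhouse-Geisser correction in every analysis, whatever Mauchly shows.
3. State that the AP-versus-manual-contact and AP-versus-no-contact conclusions rest on paired contrasts of pre-post change. Each contrast uses its own standard error and is Bonferroni-adjusted. These contrasts need no sphericity assumption.

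The cost is a few sentences and no extra data. The downside is an omnibus test that is slightly conservative when sphericity does hold: about 4.1% at n = 10 and 4.5% at n = 20 instead of 5%.

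### The hypothesis has two AP contrasts, but the plan fixes single-step Bonferroni over an undefined family; Holm on those two contrasts keeps 5% within each measure with more power

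*Protocol*

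**What the plan says.** Under Experimental conditions, the protocol states: "Treatment condition has three levels, which include the AP shoulder mobilization, a manual contact and a no-contact condition". These are "administered in random order in three separated sessions to all participants", so every participant contributes a pre-to-post change under each condition.

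Under Statistical analysis, significance is set at 0.05, with no statement of sidedness. A two-way ANOVA is planned, and "appropriate post-hoc tests of simple effects will be used" to evaluate the "hypothesis that AP mobilization produced more changes than manual contact and no-contact conditions from pre- to post-intervention". The only sentence on multiplicity within a measure is that "Bonferroni test will be used for multiple comparisons".

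The protocol does not say:
- which comparisons enter the Bonferroni family;
- whether success means beating both controls or either one;
- how many participants are planned, or for what effect or power.

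**The concern.** Three conditions give three pairs, but only two of them involve AP mobilization and carry the hypothesis. Manual contact versus no-contact is not hypothesised. If Bonferroni is run over all three pairs, each AP contrast is tested at 0.05/3 = 0.0167, and a third of the alpha goes to a question that the trial does not ask. If it is run over two, each is tested at 0.025 whatever the other one shows. In both cases a single-step rule is used where a step-down rule gives the same familywise protection over the AP contrasts.

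At stake is power for the claim the trial wants to make, that AP mobilization does better than the manual contact placebo and than no contact. A real effect is more likely than necessary to be reported as non-significant.

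**Working it through.** **Inputs from the protocol.** Alpha is 0.05; there are three conditions and two AP contrasts; each participant receives all three conditions.

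**Assumptions, because the protocol gives no figure.** Tests are two-sided. Each contrast is a paired t-test on change scores, with a standardised paired difference d = 0.6 against each control. Conditions have equal variances and covariances, so the two AP contrasts correlate at 0.5 because they share the AP session. Sample size is n = 20 or 30. The protocol states no power, so there is no figure of its own to reproduce.

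**Step 1: per-contrast level.** The level is 0.05/k, with k the size of the family: 0.05, 0.025 and 0.0167 for k = 1, 2, 3. Normal critical values are 1.960, 2.241 and 2.394.

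**Step 2: one contrast.** The noncentrality is d√n = 0.6 × √20 = 2.68. Noncentral-t power at n = 20 is 72.1% at 0.05, 60.4% at 0.025 and 53.5% at 0.0167.

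**Step 3: both contrasts.** Bonferroni needs both p-values below 0.05/k. Holm over two needs the smaller p below 0.025 and the larger below 0.05. Simulated power to beat both controls:

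| Procedure | n = 20 | n = 30 |
|---|---|---|
| Bonferroni over three pairs | 36% | 64% |
| Bonferroni over two contrasts | 44% | 71% |
| Holm over two contrasts | 56% | 81% |

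Repeat runs agree within about one point (Holm at n = 30 also came out at 80.3%). Uncorrected testing at n = 20 gives 58%, so Holm recovers nearly all of the loss.

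**Step 4: split the loss.**
- Third pair: 44 − 36 = 8 points at n = 20; 71 − 64 = 7 at n = 30.
- Single-step instead of step-down testing: 56 − 44 = 12 points; 81 − 71 = 10.

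**Step 5: dependence on n and d.** Against Holm, three-pair Bonferroni loses about 22 points at n = 12, d = 0.8; about 17 at n = 40, d = 0.5; and about 1 at n = 40, d = 0.8. The third pair alone costs at most 7 to 9 points with paired t-tests at n = 12 to 40.

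**Step 6: error within one measure.** With all conditions equal, the chance of at least one false AP claim (normal theory) is 9.1% uncorrected, 4.6% with Bonferroni over two and 3.1% with Bonferroni over three. Holm makes a first rejection exactly when two-contrast Bonferroni does, so it shares the 4.6%; a paired-t simulation at n = 20 gave 4.7%. When AP equals manual contact but no-contact differs, Holm's false AP-versus-manual-contact rate is about 5.0%.

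**The case against.** **The family is not stated.** A reader might infer from the usual all-pairs option in SPSS that three pairs and 0.0167 are planned. The protocol does not say so; its post-hoc simple effects could be other comparisons, and a SAP might define the family. This stands, and the three-pair figures are therefore conditional. The point survives without them, because Holm also improves on Bonferroni over two contrasts.

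**The whole gap of about 20 points might be blamed on counting three pairs instead of two.** The documents do not support that. The extra pair accounts for 7 to 8 points; the rest is single-step testing.

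**Bonferroni might be said to buy nothing in error control.** That is too strong. Over three pairs it protects the manual contact versus no-contact comparison and comes with matching simultaneous intervals. If all three pairs are interpreted, familywise error is 4.4% with a divisor of three and 6.4% with a divisor of two. Correction is unnecessary only if success requires beating both controls, and the protocol does not state that criterion. Holm controls error over the two AP contrasts under either criterion, but only because the third pair becomes descriptive.

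**Error across measures grows.** The protocol lists five dependent variables, which expand to ten measures (three PPT sites, two strength tests, three ROM measures, NRPS, DASH). If these were independent and all nulls true, the chance of at least one false AP claim would be 1 − (1 − 0.031)^10 ≈ 27% with three-pair Bonferroni and 1 − (1 − 0.046)^10 ≈ 38% with Holm; with correlation up to 0.6 the ranges are about 20–27% and 28–38%. This stands as a limit of the proposal. Neither Bonferroni over condition pairs nor Holm controls error across measures.

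**It is an efficiency preference.** True: the planned method is valid and conservative.

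**Conclusion.** The point holds as one of efficiency and clarity. The hypothesis has two contrasts, the family for the correction is undefined, and a single-step method is fixed where Holm gives the same 5% within each measure with at least as much power. Under the assumed d of 0.6, the gain in power to beat both controls is 12 points at n = 20 and 10 at n = 30 against two-contrast Bonferroni. Against three-pair Bonferroni, if that is what is meant, it is 20 and 17 points. These sizes depend on a sample size and effect that the protocol does not give, and the gain can be as small as about 1 point.

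The protocol's error rate is not wrong, and nothing here shows that the trial would fail.

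**What to change.** State the contrasts and the procedure, for example: for each outcome measure, the within-subject contrasts of pre-to-post change, AP mobilization versus manual contact and AP mobilization versus no-contact, are tested with Holm's procedure at two-sided 0.05; manual contact versus no-contact is reported descriptively with its 95% CI.

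A closed test (omnibus interaction at 0.05, then each pair at 0.05) should not be offered as an alternative unless the omnibus test is first specified as within-subject. The Statistical analysis section now calls treatment condition a between-subject factor, although all participants receive all three conditions.

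The change needs no further participants or measurements. Its costs are:
- Holm decisions have no matching simultaneous confidence intervals, so ordinary 95% CIs would be shown beside them;
- no confirmatory claim is available for the third pair;
- familywise control applies within each measure only, and the report should say so.

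The change should be made and dated before the data are analysed. The Participants section already describes data collection in the past tense (February to March 2018), and relaxing a multiplicity rule after seeing results would not be defensible.

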The outcome measures used in this study are: PPT, muscle strength, self-reported shoulder pain and disability, and shoulder ROM.

Pressure pain threshold (PPT)

A standardized protocol for evaluating PPT will be used.⁴⁴ One test site on the affected and non-affected shoulder (mid belly of the anterior deltoid, 5 cm caudal to the anterior border of the acromion) and one remote site on the ipsilateral tibialis anterior (5 cm inferior and 2.5 cm lateral to the tibial tubercle) will be selected for PPT measurement. All these points will be marked with a permanent marker and photographed so that the same points could be used for pre-and post-condition measures.

The PPT will be measured using an analogue Fisher algometer (Force Dial model FDK, Wagner Instruments) with a surface area at the round tip of 1cm². The algometer probe tip will be applied perpendicular to the skin at a rate of 1kg/cm²/s until the first onset of pain.¹² PPT will be measured three times on each site with a 30 s rest period between each repetition. The mean of the three measurements will be used in the statistical analysis.

Pressure algometry is a valid and reliable method to measure PPT with studies showing good repeatability of measurements on the shoulder.^{21,41}

Shoulder muscles strength

Isometric strength of the shoulder internal and external rotator musculature will be measured using a portable hand-held dynamometer (Nicholas Manual Muscle Tester, Lafayette Instruments, USA).

For external rotation testing, participants will be positioned in sitting with the shoulder in 0° of abduction and medially rotated 45° and the forearm in its mid-range of motion between supination and pronation.²⁴ The dynamometer will be placed on the lateral surface of the distal forearm just proximal to the ulnar styloid process and anchored by a belt to the handlebar of a glass suction cup on the wall. This ensured reliability when quantifying external rotation strength.²⁵ Subjects will be instructed to push in the direction of shoulder external rotation while maintaining the trunk in a stable position.

Shoulder internal rotation testing will be performed in standing using the Gerber lift-off position.¹³ The dynamometer will be placed on the distal aspect of the ventral forearm, between the patient forearm and the wall, which provided in this case the stabilization counterforce. Subjects will be instructed to lift the dorsum of the hand off the mid-lumbar region against the wall.

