Participants will be instructed to exert as much force as possible against the dynamometer during six seconds (*make test*).⁴⁹ This process will be repeated three times with a 30-s rest period between measurements and the mean will be used in the statistical analysis.

Hand-held dynamometry by using fixed instrumentation is a reliable method for measuring strength of the internal and external rotator shoulder musculature.²⁵

Self-reported shoulder pain

Participants will be asked to indicate the intensity of their current shoulder pain using a numeric rating pain scale (NRPS). The NRPS has demonstrated good test-retest reliability and responsiveness to treatment in patients with shoulder pain.³³

Shoulder disability

The Spanish version of the Disabilities of the Arm, Shoulder and Hand (DASH) questionnaire will be used to record shoulder disability.¹⁵ The DASH is comprised of 30 items (disability/symptom section) and two optional sections related to the impact of pathology on work and sports.³² Each item is scored from 1 to 5 with increasing values representing more severity of symptoms. The total score for the disability/symptoms section ranges from 30 to 150, but it is then transformed to a scale from 0 (better score possible) to 100 (worse score possible).

The Spanish version of the DASH has shown high internal consistency, excellent test-retest reliability, good construct and criteria validity and excellent responsiveness to treatment.¹⁵

Shoulder range of movement (ROM)

Active elevation in the scapular plane and passive glenohumeral internal and external rotation will be measured using a Standard BASELINE[®] 12-inch plastic goniometer following previous guidelines.^{26,39}

For measuring active elevation in the scapular plane, participants will be in a standing position. A flat stiff board will be positioned 30° anterior to the frontal plane (scaption plane) to control the plane of elevation of the affected arm.⁴² Participants will be instructed to move the affected arm into full elevation while maintaining contact with

the stiff board. The goniometer will be positioned with the fulcrum placed at the midpoint of the central aspect of the glenohumeral joint, the stable arm parallel to the trunk, and the moving arm parallel to the longitudinal axis of the humerus.²⁶

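### Eta squared is to be estimated only for significant results, so the reported effect sizes will be too large on average and non-significant outcomes will have none

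*Protocol*

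**What the plan says.** The Statistical analysis section sets significance at p < 0.05, plans a two-way ANOVA with Bonferroni comparisons, and states that "the effect size will be estimated using Eta square (η^2) when significant". It then labels values of 0.01, 0.06 and 0.14 as small, medium and large. No other effect measure is named, and descriptive statistics are mentioned only for baseline data.

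On scope, the same section says: "Five dependent variables will be considered including PPT, muscle strength, NRPS, DASH (disability/symptom section) and ROM". The Outcome measures section shows that these are ten measures:

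- PPT, 3: "One test site on the affected and non-affected shoulder", plus a remote site on the tibialis anterior.
- Strength, 2: "Isometric strength of the shoulder internal and external rotator musculature will be measured".
- NRPS, 1, and DASH, 1.
- ROM, 3: "Active elevation in the scapular plane and passive glenohumeral internal and external rotation will be measured".

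On the model: "Treatment condition has three levels, which include the AP shoulder mobilization, a manual contact and a no-contact condition". All participants receive all three conditions, yet the Statistical analysis section also says: "The between subject factor will be treatment condition". The protocol gives no sample size, power, SD or expected effect.

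**The concern.** For fixed degrees of freedom, partial eta squared is an increasing function of F. To report it only when F exceeds its critical value is to cut off the lower part of its distribution, so the mean of what is reported must exceed the mean over all trials. Outcomes that fall short get no estimate, and a reader cannot tell from the effect sizes whether such a result is near zero or merely imprecise.

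This is a rule the protocol states, not a detail it leaves to a statistical analysis plan; a plan that followed it would carry the same selection. The study's aim is to investigate the initial effects of the mobilization, and the effect sizes offered for that purpose would be a filtered set drawn from ten measures. Overstatement is worst where power is low, and nothing in the protocol shows that power will be high.

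**Working it through.** The protocol has no figure of its own to reproduce. The check asks how far the mean reported value departs from the mean over all trials.

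**Inputs from the protocol.** Three conditions, so the treatment-by-time interaction has 2 numerator df; alpha 0.05; every participant receives every condition.

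**Assumptions.** The protocol does not say which test triggers the rule, or whether classical or partial eta squared is meant. I take the interaction and partial eta squared. Each participant contributes three pre-to-post change scores with SD 1 and common correlation r. AP mobilization has a mean change d above both controls. n, d and r are varied.

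**Formulas (within-subject test).**

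- df2 = 2(n − 1)
- Noncentrality = n(2d²/3)/(1 − r)
- Sample partial eta squared = 2F/(2F + df2)
- Population value = (2d²/3)/[(2d²/3) + 2(1 − r)]

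**Smallest reportable value.** At n = 30, df2 = 58 and the critical F is 3.156, so the floor is 6.312/(6.312 + 58) = 0.098. At n = 20, df2 = 38 and the critical F is 3.245, so the floor is 6.490/(6.490 + 38) = 0.146. At n = 20 every reported value would therefore carry the protocol's label of large (0.14), whatever the truth.

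**Main illustration, n = 30, d = 0.3.** Here 2d²/3 = 0.06. For r = 0.5 the noncentrality is 30 × 0.06/0.5 = 3.6 and the population value is 0.06/(0.06 + 1) = 0.057. Integrating over the noncentral F distribution gives:

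| r | Power | Population value | Mean, all trials | Mean, significant only | Ratio | Share with none |
|---|---|---|---|---|---|---|
| 0 | 0.198 | 0.029 | 0.061 | 0.142 | 2.3 | 80% |
| 0.5 | 0.361 | 0.057 | 0.087 | 0.153 | 1.8 | 64% |
| 0.8 | 0.748 | 0.130 | 0.156 | 0.188 | 1.2 | 25% |

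The ratio isolates selection. The gap between the population value and the all-trials mean is the ordinary small-sample bias of eta squared, which is present without any selection.

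**Varying n and d at r = 0.5.**

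| n | d | All trials | Significant only | Ratio |
|---|---|---|---|---|
| 20 | 0.3 | 0.102 | 0.211 | 2.1 |
| 40 | 0.3 | 0.079 | 0.123 | 1.6 |
| 60 | 0.3 | 0.072 | 0.093 | 1.3 |
| 100 | 0.3 | 0.066 | 0.072 | 1.1 |
| 30 | 0.5 | 0.168 | 0.195 | 1.16 |
| 30 | 0.8 | 0.318 | 0.319 | 1.00 |

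Power in the last two rows is 79% and above 99%.

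**Second parameterization.** Setting the true partial eta squared at the protocol's medium value of 0.06, with within-subject df, the mean among significant results at n = 20, 30, 50 and 100 is 0.212, 0.154, 0.107 and 0.074. Over all trials it is 0.105, 0.090, 0.078 and 0.069. The share with no effect size is 74%, 62%, 40% and 10%. The pattern is the same.

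**Condition as a between-subject factor, as the protocol writes it.** The interaction F is then the one-way F on change scores with 2 and 3n − 3 df. Simulation at n = 30, d = 0.3 and r = 0, 0.5, 0.8 gives ratios of about 2.4, 2.7 and 3.0, with about 80%, 91% and 98% of tests left without an effect size. The rise with r comes from the power lost by ignoring the pairing.

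**The case against.** The strongest reply is that little is lost. The rule restricts one descriptive statistic; it alters no test, p-value or type I error. It is stated openly, so a missing eta squared can be read as p ≥ 0.05. Partial eta squared can be recomputed wherever F and its df are published, and nothing says that means or differences will be withheld. Fuller reporting could be set out in a statistical analysis plan. The size of the bias rests on assumed values, and the same calculations show it all but absent at high power. Eta squared from a 2-df omnibus test also has no direction and is not specific to AP mobilization.

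Much of this stands as a limit on severity. The figures are illustrations. The between-subject figures partly reflect a separate matter, how the condition factor is classified, and should not add weight here. The omnibus point also stands: what is inflated is the size of the condition-by-time effect, which readers will take as the evidence for the mobilization.

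The objection does not remove the defect. The direction of the bias needs no assumption about n. Recomputation depends on F being published for non-significant tests, which the protocol does not promise. A statistical analysis plan would have to depart from the protocol to correct the rule.

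**Conclusion.** The concern holds. As written, the protocol would produce effect sizes selected on p < 0.05, too large on average, and none for outcomes that miss the threshold. With n = 30 and a 0.3 SD effect, selection alone inflates mean partial eta squared 1.2- to 2.3-fold, depending on the correlation between change scores. With correlation 0.5 and the same effect, the factor runs from 2.1 at n = 20 to 1.1 at n = 100. These sizes assume that the interaction is the test meant, that eta squared is partial, and that the within-subject analysis is used; the protocol fixes neither n nor the expected effect. The consequence is for estimation and interpretation, not for the validity of the tests, so this should be corrected but does not undermine the trial's inference. The Bonferroni comparisons and the small, medium and large labels are not disputed.

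**What to change.** Delete the closing condition from the effect-size sentence, so that an effect is reported for every outcome whatever its p-value. The preferred summary is the difference in pre-to-post change, AP minus manual contact and AP minus no-contact, in original units with a 95% confidence interval. It has a direction and shows whether a non-significant result is close to null or only imprecise. This is a recommendation; the absence of intervals from the protocol is not counted as an error.

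If eta squared is kept, give it for every test, say whether it is classical or partial and which test it belongs to, and note that it is biased upward even without selection. A corrected form such as epsilon squared, (SS condition − 2 × MS error)/(SS condition + SS error), averages 0.028, 0.055 and 0.127 over all trials in the main illustration, against population values of 0.029, 0.057 and 0.130.

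The cost is one sentence of wording and a results table with ten measures and two differences each, 20 estimates in all. No new data are needed and no test changes.
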